8.1.2.5 Asthma Control Questionnaire (for Asthma/AERD/NSAID-ERD Participants Only)

The Asthma Control Questionnaire (ACQ-6) is an assessment of asthma symptoms (night-time waking, symptoms on waking, activity limitation, shortness of breath, wheezing, and short-acting beta-agonist use).

Participants are asked to recall their level of asthma control during the previous week by responding to one bronchodilator use question and 5 symptom questions.

Questions are weighted equally and scored from 0 (totally controlled) to 6 (severely uncontrolled). The mean ACQ-6 score is the mean of the responses. Mean scores of ≤ 0.75 indicate well-controlled asthma, scores between 0.75 and < 1.5 indicate partly controlled asthma, and a score ≥ 1.5 indicates not well-controlled asthma (Juniper et al 2006). Individual changes of at least 0.5 are considered to be clinically meaningful.

The questionnaire will be completed on ePRO as per SoA.

8.1.2.6 University of Pennsylvania Smell Identification Test

The University of Pennsylvania Smell Identification Test (UPSiT) is a quantitative test of olfactory function which uses microencapsulated odorants that are released by scratching standardised odour-impregnated test booklets (Doty et al 1984). Four booklets each with 10 odorants each are used for the test. Participants are asked to identify the odour using multiple choice format which lists different possibilities. The test is forced-choice, ie, the participant is required to mark one of the 4 alternatives even if no smell is perceived. Scores are based on number of correctly identified odours (score range 0 to 40).

Please note that the UPSiT smell test will be performed in all countries participating in the study except countries in which an UPSiT version in the native language is unavailable.

8.1.2.7 Patient Global Impression of Severity and Change

The Patient Global Impression of Severity (PGI-S) is a single item designed to capture the

participant's perception of overall NP symptom severity at the time of completion using a 6-point categorical response scale (0 - No Symptoms to 5 - Very Severe).

The Patient Global Impression of Change (PGI-C) instrument captures the participant's overall evaluation of response to treatment since first dose of IP. The participant is asked to report the degree to which their health status has changed using a 7-point scale (1 - Much Better to 7 - Much Worse).

Participants will complete the PGI-S and PGI-C at the site using the ePRO prior to other study procedures.

8.1.2.8 Work Productivity and Activity Impairment (WPAI) Questionnaire

The Work Productivity and Activity Impairment questionnaire (WPAI, General Health version 2.0) is a self-administered tool comprised of 6 questions which address absenteeism, presenteeism (reduced effectiveness while working), overall work productivity loss (absenteeism plus presenteeism), and activity impairment. This validated tool captures data from the past 7 days. WPAI outcomes are scored as impairment percentages, with a higher percentage indicating greater impairment and less productivity ([Reilly et al 1993](#)).

The WPAI will be completed using the eDiary in accordance with the SoA.

8.1.3 Sinus Computed Tomography

Computed tomography (CT) will be performed in all participants. Referral for baseline CT scan should be provided at V2 (Week -2) and must be performed after nasal biopsy procedure (if applicable) at V2 only if the participant has met all eligibility criteria at V2 including NPS score confirmation by central readers. At V17 (EOT/IPD), the CT scan should be performed before the nasal biopsy procedure is completed for participants in the nasal biopsy sub-study.

For participants who undergo or are planned for surgery for NP during the treatment period, a CT scan should be performed prior to the first NP surgery per the IPD visit. For participants who require SCS for the treatment of NP, a CT scan should be performed prior to the first course of SCS, if possible, and at Week 52. For participants who receive multiple NP surgeries and/or SCS treatments for NP, the CT scan should be performed prior to the first occurrence of either NP Surgery or SCS treatment for NP. For participants who discontinue IP for other reasons, a CT scan should be performed at the IPD visit as well as at Week 52, if participant opts for follow-up option 1 or 2 per Section [7.1.1](#) of the CSP. CT should only be performed at IPD visit (regardless of the reason for IPD) if at least 12 weeks have passed since the baseline CT scan.

Sinus CT images will be used to derive Lund-Mackay scores (LMSs) and Zinreich (modified Lund-Mackay) scores based on the visual assessment by independent central readers (see Section [8.1.3.1](#)), and for quantitative estimation of a sinus severity score (see Section [8.1.3.2](#))

which is representative of sinus disease burden.

The sites will remove participant-identifying information from the image data (DICOM) header prior to sending the imaging data to the central lab.

Further details on sinus CT will be available in a separate Imaging Site Guide provided to the sites. The Imaging Core Lab will outline the equipment requirements and follow an IRC. The IRC will define the logic and basis for the independent analysis methodology including the assessments to be recorded and corresponding assessment criteria to be used by the individual(s) conducting the analysis.

Sites are encouraged to consult the Study Physician and their CRA in case of any unclarity regarding timing of sinus CT during the study.

8.1.3.1 Lund-Mackay Score

The Lund-Mackay score scoring system is used to provide a semi-quantitative assessment of nasal sinuses on sinus CT scans ([Lund and Mackay 1993](#)). Based on the sinus CT images, the 5 sinuses (maxillary, anterior ethmoid, posterior ethmoid, sphenoid and frontal) on each side are scored by central radiologist as described in [Table 9](#):

Table 9 Lund-Mackay Score

Score	CT scan assessment
0	No abnormality
1	Partial opacification
2	Total opacification

The ostiomeatal complex ([Table 10](#)) is scored for right and left sides:

Table 10 Ostiomeatal Complex Score

Score	CT scan assessment
0	Not occluded
2	Occluded

The maximum total score is 24.

8.1.3.2 Quantitative Measurement of Sinus Disease Burden on Sinus Computed Tomography

Quantitative assessment of sinus CT image data will be used to derive an objective measure of sinus disease burden called sinus severity score ([Pallanch et al 2013](#)).

This is defined as:

Sinus severity score = sinus mucosal volume/
(sinus mucosal volume + sinus air volume) *100%.

The following parameters used to calculate the sinus severity score:

- sinus air volume (mL);
- sinus mucosal volume (mL).

Image analysis will be performed centrally.

8.1.3.3 Zinreich (Modified Lund-Mackay) Score

In addition to the Lund-Mackay scoring described above, the same CT images will also be scored using the modified Lund-Mackay (Zinreich) scoring system ([Okushi et al 2013](#), [Likness et al 2014](#)).

All 5 sinuses (maxillary, anterior ethmoid, posterior ethmoid, sphenoid and frontal) on each side will be scored based on the percentage of opacification from mucosal thickening according to [Table 11](#).

Table 11 Modified Lund-Mackay (Zinreich) Score

Score	Percent opacification
0	0%
1	1%-25%
2	26%-50%
3	51%-75%
4	76%-99%
5	100%

The maximum total Zinreich score is 50 (54 when including the ostiomeatal complex score described above).

Scoring will be performed centrally by the imaging core lab.

8.1.4 Post-randomisation Nasal Polyp Surgery and/or SCS Use

Participants who have a scheduled NP surgery at the time of the study enrolment and randomisation should not be randomised (refer to exclusion criterion 15). After randomisation, surgery should not be planned for the first 3 months unless emergent or deemed necessary by the PI. These cases should be discussed with the AstraZeneca study physician.

Post-randomisation nasal polyposis surgery will, by definition, define a study endpoint. Both the date the decision is made that surgery is warranted (as agreed jointly by both the

participant and the investigator), as well as the date of actual surgery (if available), will be recorded in the eCRF. NP surgery is defined as any procedure involving instruments resulting in an incision and removal of tissue (eg, polypectomy, endoscopic sinus surgery). Post-randomisation surgery procedures performed for NP during the study, including reason for surgery and information whether the surgery was performed as an outpatient or inpatient (ie, including an overnight stay in the hospital) procedure, should be recorded in the Nasal Polyp Surgery eCRF. A nasal endoscopy assessment of NPS (to provide evidence of NP recurrence), a CT scan and PROs should be performed prior to the first (post-randomisation) actual NP surgery. If no such assessment is available, a visit should be scheduled to obtain those assessments. At the time of surgery, participants will be permanently discontinued from IP and assessed as soon as possible per the EOT visit described in the SoA. If surgery is planned during the follow-up period, participants will be assessed by the Investigator and may decide to continue follow-up to the time of surgery or final visit of the study, whichever date comes first.

Rescue treatment of NP or other reasons is defined as requiring treatment with systemic corticosteroids (SCS) for at least 3 consecutive days (a single depo-injectable dose of corticosteroids will be considered equivalent to a 3-day course of systemic corticosteroids). A course of SCS is considered continuous if treatment episodes are separated by less than 7 days. Participants receiving SCS during the study should continue on IP unless the Investigator decides to withdraw the participant from IP due to safety reasons.

- If SCS is used for treatment of NP for ≥ 3 consecutive days, a CT scan and a nasal endoscopy assessment of NPS should be performed prior to first course of treatment with SCS (unless the subject has already had a CT scan prior to a NP surgery post randomisation). If no such assessment is available, an unscheduled visit should be scheduled to obtain those assessments.
- If SCS use for treatment of any other reason than NP is close to V10 (Week 24) or V17 (Week 52), the visit should be rescheduled at least 2 weeks after the last dose of SCS.
- If SCS will be used for any other reason than NP, the investigator is recommended to consult with the AstraZeneca study physician.

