Note: "Enrolled" means that a participant's, or their legally acceptable representative has agreed to participate in the clinical study following completion of the informed consent process. Potential participants who are screened for the purpose of determining eligibility for the study but are not randomly assigned in the study are considered "screen failures" unless otherwise specified by the protocol.

Intervention Groups and Duration:

Tezepelumab 210 mg will be administered SC at randomisation (Week 0) and then every 4 weeks (Weeks 4, 8, 12, 16, 20, 24, 28, 32, 36, 40, 44, 48) with an EOT at Week 52.

Matching placebo will be administered SC at the same time points. In total participants may receive up to 13 doses of the investigational product. Approximately the first 200 randomised participants will be followed up for a period of 24 weeks post EOT and the remaining randomised participants will be followed up for a period of 12 weeks after EOT visit.

All participants will have their current INCS therapy standardised to Mometasone furoate (MFNS) with a total daily dose of 400 µg or equivalent dose of INCS at Visit 1 and throughout the screening and study period. Equivalent dose should refer to the highest approved country INCS dose for CRSwNP.

Independent Adjudication Committee:

An independent adjudication committee will be established to provide an external independent assessment of blinded data to confirm the diagnosis and causality of major adverse cardiac events (MACE; to be defined in the IAC charter), serious cardiac events and deaths, as well as the diagnosis of malignancies that occur from randomisation until the end of the follow-up period; please refer to [Section 8.3.9](#).

Statistical Methods

The co-primary analysis will compare the effect of tezepelumab versus placebo in the change from baseline in NPS at Week 52 and the change from baseline in the bi-weekly mean NCS at

Week 52.

[figure not shown]

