should be checked by investigators during the study period. If a participant cannot tolerate MFNS or equivalent INCS during screening period, the participant should be screen failed.

The Principal Investigator should ask participants about SCS (oral and/or, parenteral) use for NP at each visit and record in the eCRF. Participants who require SCS and/or hospitalisation for an asthma exacerbation (see Section 8.2.5.2) or nasal polyp exacerbation during the screening period, should be screen failed and may rescreen once their symptoms improve (see Section 5.4.1).

Participants who experience an asthma exacerbation or worsening of nasal polyposis symptoms during the screening/run-in period (before Visit 2), may extend their screening period to accommodate the time needed for a short course (5-7 days) of systemic corticosteroids (SCS) treatment and return to Visit 2 no sooner than 4 weeks after the last dose of oral corticosteroids. If asthma exacerbation or worsening of nasal polyposis symptoms that require SCS or hospitalisation occurred between Visit 2 and Visit 3 (randomisation), participants should be screened failed and may be rescreened once their conditions are stabilised.

Participants will be provided with an electronic patient reported outcome (ePRO) device to record symptoms throughout the study (see Section 8.1.2). Participants who continue to meet eligibility criteria will be randomised 1:1 at Visit 3 (Day 0) to receive either placebo or tezepelumab 210 mg SC at randomisation (Week 0) and every 4 weeks thereafter (Weeks 4, 8, 12, 16, 20, 24, 28, 32, 36, 40, 44, 48). A total of 13 doses will be administered. An EOT Visit will be conducted at Week 52.

The first approximate 200 randomised participants will have a 24-week follow-up (FU) period without IP administration to assess durability of benefit. These participants will have the final safety assessment at Week 76. The remaining participants will be followed for 12 weeks after the end of treatment visit, with the final safety assessments at Week 64.

If for any reason a participant in the first set of randomised participants, as described above, is not willing to participate for a full 24-week FU period and would like to terminate participation in the study, the follow-up discontinuation (FUD) visit should be performed. The FUD visit should occur at V19 (Week 64).

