- 1 The participant should be encouraged to return for all regular clinic visits and perform all scheduled assessments (excluding IP administration and, in the case of IP discontinuation due to NP surgery, nasal endoscopy and CT) until the EOT visit at Week 52 (+/-5 days).
- 2 The participant will be offered follow-up on a monthly basis via telephone calls while continuing ePRO data collection on the handheld device at home until the participant completes the EOT visit at Week 52 (+/-5 days). The UPSIT assessments will not be completed as per SoA at home after IPD visit until the participant returns to site at the EOT visit.
- 3 If the participant cannot or does not wish to comply with any of the options above, (or any component of them such as only telephone-based visits without completion of the eDiary), the Investigator will contact the participant at 52 weeks post-randomisation. No other study assessments will be performed prior to this contact.

The EOT visit will be completed immediately in the case of subsequent early withdrawal from option 1 or 2. Participants who do not wish to have any follow-up contacts will be discontinued from the study. All discontinued participants must return the eDiary at the EOT visit.

If the participant chooses option 1, all assessments will be completed as per the SoA as indicated in [Table 1](#). If the participant chooses option 2 or 3, the key information to be collected during the telephone calls are AEs/SAEs, changes in concomitant medication, health

care utilisation, and asthma exacerbation information (asthma/AERD/NSAID-ERD participants). Participants who initially choose options 1 or 2 and subsequently cannot or do not wish to comply with the requirements of their option can continue with a less intensive option (ie, participant initially choosing option 1 can continue with options 2 or 3, participants initially choosing option 2 can continue with option 3). Participant Withdrawal from the Study

A participant may withdraw from the study at any time at his/her own request or may be withdrawn at any time at the discretion of the investigator for safety, behavioural, compliance, or administrative reasons. This is expected to be uncommon.

A participant who considers withdrawing from the study must be informed by the Investigator about modified follow-up options (eg, telephone contact, a contact with a relative or treating physician, or information from medical records).

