8.3 Adverse Events and Serious Adverse Events

8.3.1 Time Period and Frequency for Collecting AE and SAE Information

Adverse events and Serious Adverse Events will be collected from time of signature of informed consent form throughout the treatment period and including the follow-up period.

All SAEs will be recorded and reported to AstraZeneca or designee within 24 hours, as

indicated in [Appendix B](#). The Investigator will submit any updated SAE data to AstraZeneca within 24 hours of it being available.

If the investigator becomes aware of a serious adverse event with a suspected causal relationship to the investigational medicinal product that occurs after the end of the clinical study in a participant treated by him or her, the investigator shall, without undue delay, report the serious adverse event to the sponsor.

The method of recording, evaluating, and assessing causality of AE and SAE and the procedures for completing and transmitting SAE reports are provided in [Appendix B](#).

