8.3.9 Independent Adjudication Committee

An IAC will be established in the study to provide an external independent assessment of blinded data to confirm the diagnosis and causality of major adverse cardiac events (MACE; defined in the IAC charter), serious cardiac events, and deaths, as well as diagnosis of malignancies that occur from randomisation until the end of the follow-up period. Details on

the adjudication process, including score of adjudication and the committee membership, will be included in the Adjudication Committee Charter/Manual of Operations.

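### Protocol 8.1.4 lets off-treatment follow-up end at polyp surgery, which conflicts with safety collection to the final visit and can drop worst outcomes from the durability analysis

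*Protocol*

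**What the plan says.** **Surgery in follow-up.** Protocol 8.1.4 states that participants with surgery planned in the follow-up period are assessed by the investigator and "may decide to continue follow-up to the time of surgery or final visit of the study, whichever date comes first".

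**Length of follow-up.** Dosing is "every 4 weeks (Weeks 4, 8, 12, 16, 20, 24, 28, 32, 36, 40, 44, 48) with an EOT at Week 52" (Synopsis). Under 4.1, the first 200 or so randomised have 24 weeks of follow-up: "These participants will have the final safety assessment at Week 76". For the others: "The remaining participants will be followed for 12 weeks after the end of treatment visit, with the final safety assessments at Week 64". Section 4.1 and the Schedule of Activities add that one of the first 200 who does not want the full 24 weeks has a follow-up discontinuation visit at Week 64.

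**Safety collection.** Under 8.3.1, AEs and SAEs "will be collected from time of signature of informed consent form throughout the treatment period and including the follow-up period". Under 8.3.9, the adjudication committee reviews cardiac events, deaths and malignancies "that occur from randomisation until the end of the follow-up period". After the study ends, 8.3.1 requires reporting only of SAEs suspected to be related to study drug that come to the investigator's attention.

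**Surgery on treatment.** Section 7.1.1 takes a different line. Study drug stops, but the participant is encouraged to attend all visits to Week 52, "excluding IP administration and, in the case of IP discontinuation due to NP surgery, nasal endoscopy and CT".

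**Analysis.** SAP 2.1.3 admits a participant to the Additional FU Analysis Set only if the Week 64 visit is completed. SAP 4.2.9.1 analyses NPS and NCS up to Week 76 in that set, and in Step V gives scores after surgery the worst possible value.

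**The concern.** Surgery after stopping treatment is one of the outcomes that off-treatment follow-up exists to observe. If it also ends follow-up, observation stops because of the outcome. Two things are at stake.

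- **Safety.** Collection may close before the scheduled final assessment in participants whose disease has returned badly enough to need surgery. Non-serious AEs, and SAEs not suspected to be related, that start after surgery would then have no route into the database.
- **Durability.** The SAP intends surgery to count as the worst result. A participant who leaves at surgery before Week 64 fails the entry condition of the analysis set, so that score is never assigned. If surgery rates differ between arms off treatment, the omission is unequal.

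**Working it through.** **1. Schedule.** Inputs: 13 doses, Weeks 0 to 48; end of treatment Week 52; follow-up 12 or 24 weeks.

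- 52 + 12 = Week 64, the plan's own final visit; 64 − 48 = 16 weeks after last dose.
- 52 + 24 = Week 76, again as stated; 76 − 48 = 28 weeks after last dose.

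**2. Shortfall if follow-up ends at surgery in Week s.** Weeks after last dose = s − 48; shortfall to Week 64 = 64 − s.

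| Surgery week | Weeks after last dose | Short of Week 64 by |
|---|---|---|
| 52 | 4 | 12 |
| 54 | 6 | 10 |
| 58 | 10 | 6 |
| 62 | 14 | 2 |
| 64 or later | 16 or more | 0 |

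Surgery between Weeks 64 and 76 affects only the first 200, who can lose up to 12 of their planned 28 weeks.

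**3. Illustrative number, Weeks 52 to 64.** Protocol 9.2 assumes 11% of placebo participants with a surgery decision by Week 52 and a hazard ratio of 0.33. As a check on these inputs, they imply 200 × 0.11 + 200 × (1 − 0.89^0.33) = 29.5 events and 85% power at the 5% level, consistent with the stated minimum of 80%. The assumption here is that the same constant hazard continues off treatment.

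- Placebo: 1 − 0.89^(12/52) = 2.65%; × 200 = 5.3.
- Tezepelumab, hazard ratio still 0.33: 1 − 0.89^(0.33 × 12/52) = 0.88%; × 200 = 1.8. Total about 7 of 400.
- Tezepelumab, effect lost (hazard ratio 1): 5.3. Total about 11 of 400.
- Placebo rate varied from 5% to 20%: about 3 to 13 of 400 at hazard ratio 0.33, and about 5 to 20 at hazard ratio 1.

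Each case loses about 6 weeks on average. At 11% and hazard ratio 0.33 that is 32.0 + 10.6 = 42.6 of 400 × 12 = 4,800 person-weeks, or 0.9% (0.4% to 1.7% over placebo rates of 5% to 20%).

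**4. Durability analysis.** Take two of the first 200, both with surgery at Week 58. One attends Week 64, enters the Additional FU Analysis Set and scores 8 for NPS and 3 for NCS after surgery. The other stops at surgery as 8.1.4 allows, never completes Week 64 and is not in the set. The outcome is the same; only the first counts.

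With about 100 per arm among the first 200, the expected number leaving the set is 2.65 + 0.88 = about 3.5, or 2 × 2.65 = about 5 if the effect is lost. Dropping a fraction f who would score 8, from an arm whose other members average m, lowers the arm's mean NPS by f × (8 − m). With f = 0.0265 and m assumed between 2 and 6, that is 0.16 to 0.05 points.

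**The case against.** The 8.1.4 sentence is permissive and sits under efficacy assessments. AE collection is governed by 8.3.1 and the Schedule of Activities, which lists AEs at Week 64 for everyone. Surgery is not among the stated reasons for study withdrawal, and anyone considering withdrawal must be told about lighter follow-up such as telephone contact or medical records. AEs already reported are followed to resolution or stabilisation (8.3.2). The first 200 arguably have a floor at the Week 64 discontinuation visit. Section 7.1.1 concerns the period before the Week 52 endpoints, so a different rule afterwards may be deliberate.

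Much of this stands. A reader might infer that safety data are never collected after follow-up surgery; the text says only that follow-up may end there. A reader might also infer a breached 16-week AE window, but the documents state none. The 16 weeks follow from the visit schedule; the explicit 16-week periods concern contraception, blood donation and partner pregnancy. Nor does every relapse end follow-up: relapse treated with systemic steroids alone does not. Adding surgery in Weeks 64 to 76 would raise the count, but those participants already have 16 weeks. The first follow-up surgery itself is not lost, because follow-up runs to it and both the decision and surgery dates are recorded.

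The conflict remains. The first-come wording makes surgery the latest end point, and nothing says that AE collection stays open past it. The Week 64 discontinuation visit is written for unwillingness to complete 24 weeks; 8.1.4 does not refer to it, and the other half of the trial has no such rule. Individual time at risk in the exposure-adjusted rates corrects for shorter observation, not for its dependence on outcome.

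**Conclusion.** The point holds as an inconsistency to be reconciled, with a small but outcome-dependent effect. Section 8.1.4 allows an end of follow-up that 8.3.1, 8.3.9 and the Week 64 and 76 assessments do not foresee, and the SAP's entry condition then removes participants whom its scoring rule was meant to keep.

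The expected size is about 7 to 11 of 400 in Weeks 52 to 64, and about 4 to 5 of the first 200 leaving the durability set. This rests on carrying an on-treatment rate forward at constant hazard. It also uses surgery decisions, whereas 8.1.4 turns on the surgery date, so the true number is lower if surgery lags the decision.

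The co-primary and key secondary endpoints run only to Week 52 and are unaffected. On-treatment AE summaries, which close 33 days after last dose (Day 337 + 33 = Day 370, just after Week 52), are almost untouched. The exposed results are on-study and post-treatment safety, and off-treatment NPS and NCS. Steroid use after a follow-up surgery could also go unrecorded, but that analysis is in an exploratory plan not available here.

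**What to change.** **Protocol 8.1.4.** Reconcile it with 8.3.1, 8.3.9 and 7.1.1 by stating that participants who have polyp surgery in follow-up are asked to remain in the study to their scheduled final visit (Week 64 or 76) for AEs and SAEs, concomitant medication and health resource use, with no endoscopy required after surgery. This concerns data collection only.

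**SAP 2.1.3.** Keep participants among the first 200 who have follow-up surgery before Week 64 in the Additional FU Analysis Set whether or not they complete that visit, with the worst possible score after surgery as 4.2.9.1 already provides. No post-surgery measurement is needed for this.

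**Cost.** One protocol sentence and one SAP line, using visits and calls already scheduled. The downside is that a few participants continue these after surgery. If amendment is no longer practical, the study report should give, by arm, how many follow-ups ended at surgery, when, and how many participants left the set for that reason.
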